5.7.1.2 QTc Withdrawal Criteria

A subject that meets the criteria below will be withdrawn from the study.

- QTcB or QTcF > 500 msec or uncorrected QT >600msec (machine or manual overread)
- If subject has bundle branch block then criteria is QTcB or QTcF > 530 msec

These criteria are based on an average QTc value of triplicate ECGs. If an ECG demonstrates a prolonged QT interval, obtain 2 more ECGs over a brief period, and then use the averaged QTc values of the 3 ECGs to determine whether the subject should be discontinued from the study.

5.8 Follow-Up

At treatment discontinuation, subjects will undergo a safety assessment approximately 28 days (+/- 4 days) post the last dose of protocol therapy. Thereafter, follow-up will be required every three months until next therapy, relapse or death, whichever comes first (see off study evaluations per the Schedule of Assessments, Section 2).

6 Adverse events

6.1 Adverse Events:

Any untoward medical occurrence in a subject or clinical investigation subject, temporally associated with the use of a medicinal product, whether or not considered related to the medicinal product.

Events meeting the definition of an AE include:

- Any abnormal laboratory test results (hematology, clinical chemistry, or urinalysis) or other safety assessments e.g., ECGs, radiological scans, vital signs measurements), including those that worsen from baseline, and felt to be clinically significant in the medical and scientific judgment of the investigator

- Exacerbation of a chronic or intermittent pre-existing condition including either an increase in frequency and/or intensity of the condition
- New conditions detected or diagnosed after investigational product administration even though it may have been present prior to the start of the study
- Signs, symptoms, or the clinical sequelae of a suspected interaction
- Signs, symptoms, or the clinical sequelae of a suspected overdose of either investigational product or a concomitant medication (overdose per se will not be reported as an AE/SAE)

“Lack of efficacy” or “failure of expected pharmacological action” per se will not be reported as an AE or SAE. However, the signs and symptoms and/or clinical sequelae resulting from lack of efficacy will be reported if they fulfill the definition of an AE or SAE.

Events that **do not** meet the definition of an AE include:

- Any clinically significant abnormal laboratory finding or other abnormal safety assessments that is associated with the underlying disease, unless judged by the investigator to be more severe than expected for the subject’s condition.
- The disease/disorder being studied, or expected progression, signs, or symptoms of the disease/disorder being studied, unless more severe than expected for the subject’s condition
- Medical or surgical procedure (e.g., endoscopy, appendectomy); the condition that leads to the procedure is an AE
- Situations where an untoward medical occurrence did not occur (social and/or convenience admission to a hospital)
- Anticipated day-to-day fluctuations of pre-existing disease(s) or condition(s) present or detected at the start of the study that do not worsen
- B cell depletion and hypogammaglobulinemia due to ofatumumab treatment

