This is a phase 2, open-label, single institution trial of combination of intravenous (IV) ofatumumab and oral GSK2110183 in patients with relapsed or refractory CLL. Patients must have received at least one prior line of therapy containing fludarabine (single-agent or combination therapy). During the initial 7 months Treatment Phase, ofatumumab will be administered weekly for 8 doses, then once every 4 week cycle for an additional 4 doses (dose and schedule identical to the pivotal phase 2 trial) (Wierda 2010) and GSK2110183 will be given daily PO (Treatment Phase). There will be an initial 10 day lead-in with GSK2110183 alone prior to initiation of ofatumumab to allow for evaluation of changes in cell surface expression due to GSK2110183 and for GSK2110183 pharmacokinetic studies (Lead-in Phase). The official Cycle 1 Day 1 will start on the date of first dose of ofatumumab. Cycle duration = 4 weeks. Patients will be assessed for safety, disease assessment, response, and survival on day 1 of each cycle during the Treatment Phase. The safety data will be reviewed by the Data Safety Monitoring Board (DSMB) during their biannual meeting. Enrollment will continue while DSMB response to the review of the safety data is awaited. All patients achieving SD, PR or CR by the end of the Treatment Phase will proceed to the Maintenance Phase. Patients with PD at any time, including by the end of Treatment Phase, will be taken off study. During the Maintenance Phase,

single-agent GSK2110183 will be administered daily for a maximum of 12 months (12 cycles). Maximum duration on any study drug is 18 months (18 cycles). During the Follow-up Phase, patients will be assessed for safety, disease assessment, response, and survival every 3 months through month 36 (year 3), or until subsequent CLL therapy or death, whichever comes first. Key indications for study withdrawal are progressive disease, intolerable toxicity, or completion of therapy.

G - GSK2110183 125mg OD continuously

O - Ofatumumab: The dosage regimen is 300mg Ofatumumab for the first infusion and 2,000 mg ofatumumab for all subsequent infusions. The infusion schedule is 8 consecutive weekly infusions, followed 4 weeks later by 4 consecutive monthly (i.e. every 4 weeks) infusions.

* PK sampling on Day 10 of lead-in phase and with 8th weekly dose of ofatumumab

STUDY ENDPOINTS

Primary:

- Overall Response Rate (ORR)

Secondary:

- Stable disease duration
- If responses are observed, response duration

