- Progression-free survival
- Overall survival
- Toxicity (as graded per NCI CTC version 4.03)

STUDY DURATION:

- Completion of 18 cycles (months) plus Lead-in of 10 days
- At any time for unacceptable toxicity or patient request

TOTAL SAMPLE SIZE:

31 response evaluable patients

DOSING REGIMEN (S):

GSK2110183 125mg OD continuously in combination with Ofatumumab 300mg IV for the first infusion and 2000mg weekly x 7 doses, followed 4 weeks later by 4 consecutive monthly (i.e. every 4 weeks) doses.

DRUG SUPPLIES:

GSK will supply GSK2110183 oral tablets and ofatumumab IV formulation

2 Schedule of Study Assessments *

Procedures	Screening ≤ 28 days from Lead-in Day 1	Lead-in phase (Days 1 to 10)			Treatment Phase Cycles 1 and 2				Cycles 3	Cycles 4-7	Maintenance Phase		Follow-up Every 3 months up to 36 months
		Day 1	Day 8	Day 10	Day 1	Day 8	Day 15	Day 22			Day 1	Day 1	
Informed Consent	X												
Demography	X												
Record prior medications, treatments, including prior anti-cancer therapies	X												
Physical Exam	X	X			X				X	X	X	X	X
Neurological symptoms questions assessment	X	X			X				X	X	X	X	X
ECOG	X	X			X				X	X	X	X	X
Height	X	X											
Weight	X	X			X				X	X	X	X	X
Vital Signs(BP, Pulse, RR, SaO2, temp) ¹	X	X			X	X	X	X	X	X	X	X	
Tumor measurements by physical exam (lymphadenopathy, spleen/liver)	X	X			X				X	X	X	X	X
Bone marrow aspirate ± biopsy ²	X		X									X	
CT chest, abdomen, pelvis ³	X										X	X	
12-lead ECG ⁴	X												
Adverse Events	X	X			X	X	X	X	X	X	X	X	X
Concomitant Therapy	X	X			X	X	X	X	X	X	X	X	
Hematology ⁵	X	X			X	X	X	X	X	X	X	X	X
Reticulocyte count	X												
HbA1C	X												
INR/PT	X												
PTT	X												
Direct Antiglobulin Test	X												
Beta 2 microglobulin	X												
CD4/CD8 cell count	X											X	
Chemistry ⁶	X	X			X	X	X	X	X	X	X	X	X
Urinalysis	X												

Serum Pregnancy Test	X												
TSH	X							X ¹²	X ¹²	X ¹²	X ¹²		X
Hepatitis B&C ⁷	X				X		X	X	X	X	X		X
Quantitative serum immunoglobulins ⁸	X							X ⁸	X ⁸	X ⁸	X ⁸		X ⁸
Peripheral blood for FISH	X ¹³												
Pharmacokinetic blood sampling ⁹				X			X						
Peripheral blood for correlative studies and ZAP70, and IgVH mutational status	X			X ¹⁰									
Dispense GSK2110183 for next cycle ¹¹		X			X				X		X	X	
Ofatumumab infusions ¹⁴					X	X	X	X		X			
Follow-up anti-cancer therapy													X
Follow-up survival													X

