5.3 Visit schedule and assessments

Screening Assessments and all on study scheduled visits and assessments are outlined in Section 2 Schedule of Study Assessments.

An unscheduled visit can occur at any time during the study. The date for the visit and any data generated must be recorded on the appropriate CRF. Source documents for these unscheduled visits must also be maintained.

At treatment discontinuation, subjects will undergo off study evaluations as per the Schedule of Assessments, Section 2. In addition, a safety assessment will be done approximately 28 days (+/- 4

days) post the last dose of protocol therapy. Thereafter, for patients who go off protocol treatment will be followed every three months to document time to relapse, next treatment, and death.

Pharmacokinetic sampling will take place on the following schedule (Appendix 6):

- Day 10 of the Lead-in Phase:
 - o Predose (before GSK2110183 dose), 0.5, 1, 2, 3, 4, 6, 8, 10-12, 14-22, and 24hr after (10-12hr and 14-22hr samples only where collection times are feasible)

- Cycle 2 Day 22 of the Treatment Phase (with 8th weekly dose of ofatumumab):
 - o Predose (before GSK2110183 dose), 0.5, 1, 2, 3, 4, 6, 8, 10-12, 14-22, and 24hr after (10-12hr and 14-22hr samples only where collection times are feasible)

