6.2 Serious Adverse Event (SAE) Definition

A serious adverse event is one that at any dose (including overdose):

- Results in death
- Is life-threatening¹

- Requires inpatient hospitalization or prolongation of existing hospitalization
- Results in persistent or significant disability or incapacity²
- Is a congenital anomaly or birth defect
- Is an important medical event³

¹“Life-threatening” means that the subject was at immediate risk of death at the time of the serious adverse event; it does not refer to a serious adverse event that hypothetically might have caused death if it were more severe.

²“Persistent or significant disability or incapacity” means that there is a substantial disruption of a person’s ability to carry out normal life functions.

³Medical and scientific judgment should be exercised in deciding whether expedited reporting is appropriate in situations where none of the outcomes listed above occurred. Important medical events that may not be immediately life-threatening or result in death or hospitalization but may jeopardize the patient or may require intervention to prevent one of the other outcomes listed in the definition above should also usually be considered serious. Examples of such events include allergic bronchospasm requiring intensive treatment in an emergency room or at home, blood dyscrasias or convulsions that do not result in inpatient hospitalization, or the development of drug dependency or drug abuse. A new diagnosis of cancer during the course of a treatment should be considered as medically important.

NOTE: Pregnancies must be reported to GSK; however are not to be reported as SAEs unless they meet serious criteria.

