10.2 Endpoints

The primary and secondary objectives will be evaluated by analysis of efficacy endpoints (response rates, response duration), progression-free and overall survival, and toxicity.

Evaluable for toxicity - All patients will be evaluable for toxicity from the time of their first dose of GSK2110183. After 6 subjects have completed cycle 1 of the Treatment Phase (on combination ofatumumab and GSK2110183), an analysis to assess safety and tolerability will be conducted.

Evaluable for response - All patients who have received at least 1 dose of GSK2110183 during the initial Lead-in Phase will be considered evaluable for response. Duration of Response (DOR) is defined, for the subset of patients with a CR or PR, as the time from first documented evidence of CR or PR until first documented disease progression or death due to any cause. If sample size permits, duration of response will be summarized descriptively using Kaplan-Meier medians and quartiles. Only the subset of patients who show a CR or PR will be included.

Evaluable for survival - All patients will be evaluable for survival. Overall survival is defined as the length of time between the date of first dose of study treatment (GSK2110183) and death due to any cause. Progression Free Survival (PFS) is defined as the length of time between the date of first dose of study treatment (GSK2110183) and the earliest date of disease progression or death due to any cause. If the patient does not have a documented date of progression or death, then PFS will be censored at the date of last adequate assessment. For a patient who is alive at the time of the statistical analysis, the patient will be considered censored at the last date of known contact.

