10.3.3 Statistical Analysis

Univariate analysis of response predictors will be performed using Fisher's exact test and Wilcoxon rank-sum test. Response predictors to be evaluated will include age, abnormal baseline serum laboratory values (e.g. LDH, beta-2 microglobulin, albumin, direct antiglobulin test, hemoglobin, lymphocytes, neutrophils, platelets, creatinine, ZAP70, CD38), clinical features (bulky adenopathy, organomegaly, RAI stage), disease status (relapsed or refractory), number of prior lines of therapy (1,2, vs 3 or more), FISH cytogenetics (17p/11q deletion vs none), IgVH status (mutated versus unmutated). Survival will be calculated using the Kaplan-Meier method. Statistical analyses will be applied using SAS 9.2.

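### Sections 5.8, 5.1/synopsis and 5.3 disagree on when follow-up ends, so deaths needed for overall survival are only partly required to be collected

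*Combined protocol and SAP*

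**What the plan says.** The follow-up rule appears in four places.

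- **Section 5.8:** after the 28-day safety assessment, "follow-up will be required every three months until next therapy, relapse or death, whichever comes first". There is no month-36 limit. The section refers to the Section 2 schedule.
- **Synopsis (Study Design) and Section 5.1:** assessments "every 3 months through month 36 (year 3), or until subsequent CLL therapy or death, whichever comes first". Relapse is not named as a stop.
- **Section 5.3:** patients off protocol treatment "will be followed every three months to document time to relapse, next treatment, and death". There is no first-event stop and no month limit.
- **Section 2 schedule:** a follow-up column every 3 months up to 36 months, with a row for anti-cancer therapy and a row labelled "Follow-up survival". It does not say whether contact continues after relapse or next therapy.

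On analysis, Section 10.2 defines overall survival (OS) from the first GSK2110183 dose to death from any cause and states "All patients will be evaluable for survival". For a patient alive at analysis, "the patient will be considered censored at the last date of known contact". Section 10.3.3 adds: "Survival will be calculated using the Kaplan-Meier method". Section 4.1.2 lists time to next CLL therapy among the secondary objectives, but it is not in the endpoint lists or Section 10.

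**The concern.** OS as defined in 10.2 needs the date of every death within the observation period, including deaths after relapse and after the next line of treatment. Two of the three rules allow contact to end before then, at an event that is itself related to the risk of death. Kaplan-Meier assumes that a censored patient has the same later risk as those still followed. If patients are censored because they relapsed or started new therapy, that assumption probably fails.

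Time to next CLL therapy is also exposed, but only under 5.8 and only for patients who relapse before they are treated again.

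**Working it through.** **1. The plan's own calculation.** The only design calculation is the response rule in 10.3.2. With 31 patients, P(X ≥ 19 | p = 0.47) = 0.0786 and P(X ≤ 18 | p = 0.67) = 0.1915, which match the stated 0.079 and 0.192. That rule does not use follow-up after relapse. The plan gives no OS sample size, event count or precision to check.

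**2. The rules applied to one patient.** Take a patient who relapses at month 10, untreated at that point, starts new CLL therapy later and then dies before month 36.

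| Rule | Required contact ends | Next-therapy date required? | Death required? |
|---|---|---|---|
| 5.8 | month 10 | no | no |
| 5.1 / synopsis | start of new therapy | yes | no |
| 5.3 | death | yes | yes |

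**3. The SAE backstop.** An event that "Results in death" is an SAE (6.2). Under 6.4.1, SAEs are collected for at least 6 months after the last dose, or to the end of follow-up if that is longer. The 6-month minimum holds under every rule; any extension depends on the term in dispute. Reporting stops once another therapy begins (6.4.1), and expected disease progression need not be reported (6.3.2). SAE reporting therefore recovers some of the missing deaths, but not all.

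**4. Possible size (all inputs assumed).** In an exponential illness-death model, let *l* = ln 2 / median PFS, *d* = share of first events that are deaths, *m* = ln 2 / median post-relapse survival, and *v* = ln 2 / median time from relapse to next therapy. The post-relapse death rate is assumed unchanged by next therapy.

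- True OS: S(t) = exp(-lt) + (1-d)·l·[exp(-mt) - exp(-lt)]/(l-m).
- Kaplan-Meier under 5.8 with no SAE capture: exp(-d·l·t).
- Under 5.8 with SAE capture, and under 5.1: integrate the hazard (d·l·P0 + m·P1)/(P0 + P1). P0 is alive without relapse; P1 is relapsed, alive and not yet on next therapy, and for SAE capture also within 6 months of relapse.

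*Upward example* (PFS 8 months, d = 20%, post-relapse 24, next therapy 4): l = 0.0866, m = 0.0289. True S(24) = 0.125 + 0.8 × 0.0866 × (0.5 - 0.125)/(0.0866 - 0.0289) = 0.125 + 0.450 = 0.575. Under 5.8 without capture, exp(-0.2 × 0.0866 × 24) = 0.660. With SAE capture the value is 0.623, and under 5.1 it is 0.611. Deaths by month 36 that are observed: 33%, 46% and 51%.

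*Downward example* (PFS 6, d = 20%, post-relapse 36, next therapy 4): true 0.607; the three rules give 0.574, 0.589 and 0.595.

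The sign depends on whether the post-relapse death rate m exceeds the pre-relapse death rate d·l. In the upward example m = 0.0289 against d·l = 0.2 × 0.0866 = 0.0173. In the downward example m = ln 2/36 = 0.0193 against d·l = 0.2 × ln 2/6 = 0.0231.

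*Grid at month 24:* PFS 6, 8, 12, 18; d 10, 20, 30, 50%; post-relapse 9, 15, 24, 36; next therapy 2, 4, 8 (no role in the first row). Bias is Kaplan-Meier minus true OS, in percentage points; exact ties are not counted as upward.

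| Rule | Scenarios | Bias range | Median bias | Upward | Deaths by month 36 observed (median) |
|---|---|---|---|---|---|
| 5.8, no SAE capture | 64 | -15 to +44 | +10 | 52 | 11.5% to 75% (37%) |
| 5.8, 6-month SAE capture | 192 | -12 to +24 | +6 | 156 | 27% to 81% (51%) |
| 5.1 / synopsis | 192 | -11 to +23 | +4 | 156 | 28% to 86% (59%) |

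The bias exceeds 5 points in either direction in 117 of 192 scenarios in the second row and 89 of 192 in the third.

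The SAE row assumes that the last dose falls at relapse and that every such death is reported. Less is captured if relapse comes after the last dose or a death is treated as expected progression; more is captured if treatment continues past progression, which 5.7 allows.

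**5. Scale.** With 31 patients and complete follow-up, the 95% half-width near 0.575 is 1.96 × √(0.575 × 0.425/31) = 0.174, or about 17 points.

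**The case against.** The best counter-reading is that 5.3 is not a stopping rule but a statement of what must be documented. On that view 5.8 and 5.1 end required visits, while 5.3 and the survival row in the schedule still require death dates, and data are lost only at a site that ignores 5.3. This is possible, and no section forbids later contact. But it asks the site to set aside an explicit first-event stop in 5.8 and 5.1 in favour of a more general sentence elsewhere. The synopsis and 5.1 also take patients with progressive disease off study, which makes an early stop a natural reading.

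Section 10.5 promises to describe follow-up times and report losses. That would make truncated follow-up visible, but it would not recover the deaths.

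Timing matters too. Section 9.1 analyses data once accrual is complete and leaves later data to a follow-up report. On the same grid at month 12, the median bias is only +1.6 points (5.8 with SAE capture) and +1.2 (5.1), and it exceeds 5 points in 21 and 17 of 192 scenarios. The larger figures therefore bear mainly on the later report.

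Finally, the grid is arbitrary and equally weighted, so its counts are not probabilities. That is correct: the figures show what could happen, and the contradiction does not depend on them.

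**Conclusion.** The concern holds. Three follow-up rules conflict on the face of the text, the schedule does not settle them, and under two of them deaths that the OS definition needs are only partly required. How much is lost depends on which rule the site applies.

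If contact does stop at relapse or next therapy, OS would most likely be overstated. The size and even the sign rest on assumed event rates. In the assumed grid the median bias is smaller than the sampling error, but unlike sampling error it would not average out.

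The consequence is confined to secondary results: OS and, under 5.8, time to next CLL therapy. No decision rule rests on OS. It is still worth correcting, because dates not collected during follow-up may be hard to recover later.

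**What to change.** Reconcile 5.8, 5.1 and the synopsis with 5.3 and the Section 2 schedule by separating two things.

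- **Disease assessment:** may stop as planned, but the sections should agree on whether relapse ends it. PFS and response duration both end at progression, so either choice leaves OS intact.
- **Vital status and date of next CLL therapy:** collected every 3 months through month 36 for every treated patient, regardless of relapse, next therapy or treatment discontinuation, unless consent is withdrawn. This should expressly cover patients taken off study for progressive disease.

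Keep the 10.2 rule that censors living patients at last known contact; it works once contact no longer depends on disease course.

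The cost is a wording change in 5.8, 5.1 and the synopsis, plus a short phone or chart contact each quarter for about 31 patients. The schedule already has the rows.

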daily recommended phase 2 dose of GSK2110183 will be used. As neither ofatumumab nor GSK2110183 are myelosuppressive, the combination is anticipated to be well-tolerated in a relapsed or refractory CLL population where cytopenias are common. Currently, neither ofatumumab nor GSK2110183 are available for use in Canada. Although rituximab is approved for first line use as part of the FCR (fludarabine, cyclophosphamide, rituximab) regimen, retreatment using rituximab is not available. Furthermore, access to alemtuzumab in Ontario is restricted (no funding) and rarely available. As a result, there are limited options for therapy in CLL patients failing fludarabine therapy in Ontario and there is heavy demand from community oncologists and patients for clinical trials that provide novel therapies. Currently at Princess Margaret Cancer Centre, the largest tertiary care oncology centre in Canada, we have no competing trials for CLL patients who are relapsed or refractory to prior fludarabine-based therapy, and therefore accrual to this proposed study is anticipated to be rapid and efficient.

STUDY OBJECTIVES:Primary:

1. To assess the efficacy (overall response rate, including complete and partial responses as per the IWCLL 2008 response criteria) of ofatumumab in combination with GSK2110183 in the treatment of patients with relapsed or refractory CLL who have received at least one prior fludarabine-containing regimen.

[figure not shown]
Secondary:

1. To assess the toxicity of ofatumumab in combination with GSK2110183 in patients with relapsed or refractory CLL.
2. To assess clinical efficacy endpoints such as progression-free and overall survival, stable disease, response duration, and time to next CLL therapy following therapy with ofatumumab in combination with GSK2110183.
3. To identify predictors of response using gene expression analysis and demonstrate target inhibition via flow-cytometry based pharmacodynamic studies.
4. To evaluate the pharmacokinetics of GSK2110183 after multiple single agent daily dosing and in combination with ofatumumab in first 10 eligible participants.

STUDY DESIGN:

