6.3.1 Laboratory and Other Safety Assessment Abnormalities Reported as AEs and SAEs

- Any abnormal laboratory test results (hematology, clinical chemistry, or urinalysis) or other safety assessments (e.g., ECGs, radiological scans, vital signs measurements), including those that worsen from baseline, and felt to be clinically significant in the medical and scientific judgment of the investigator **are** to be recorded as AEs or SAEs.

- All events meeting liver stopping criteria must be recorded as an SAE.
- However, any clinically significant safety assessments that are associated with the underlying disease, unless judged by the investigator to be more severe than expected for the subject's condition, are **not** to be reported as AEs or SAEs.
- B cell depletion, IgG below LLN, low CD19+ count, and hypogammaglobulinemia due to treatment with ofatumumab are **not** to be reported as AEs or SAEs.
- Infusion related AEs may lead to a prolonged infusion time. Overnight stay at the hospital due to slow infusion rate is **not** to be reported as a SAE.

The investigator must appraise all abnormal laboratory results for their clinical significance. If any abnormal laboratory result is considered clinically significant, the investigator must provide details about the action taken with respect to the test drug and about the patient's outcome.

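### Hematologic toxicity is reported only through adverse events, which may leave out cytopenias attributed to CLL; the blood counts already collected should also be graded and tabulated

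*Combined protocol and SAP*

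**What the plan says.** - **Endpoint.** Section 4.2.2 defines safety by the type, frequency, severity and treatment relationship of adverse events.
- **What counts.** Section 6.1 includes "Any abnormal laboratory test results (hematology, clinical chemistry, or urinalysis) or other safety assessments", and adds "including those that worsen from baseline, and felt to be clinically significant" in the investigator's judgment.
- **What does not count.** The same section then excludes "Any clinically significant abnormal laboratory finding or other abnormal safety assessments that is associated with the underlying disease", with the exception "unless judged by the investigator to be more severe than expected" for that subject's condition. Section 6.3.1 applies the same rule to AE and SAE reporting: "any clinically significant safety assessments that are associated with the underlying disease, unless judged by the investigator to be more severe than expected".
- **Analysis.** Section 10.2 states "All patients will be evaluable for toxicity from the time of their first dose of GSK2110183". Section 10.4 takes everyone who received any protocol therapy, grades adverse events by CTCAE 4.03, requires causality for each drug separately, and plans a safety review after 6 patients complete Cycle 1. Section 10.3.3 covers response predictors and survival. None of these sections grades or tabulates laboratory values.
- **Population.** The Synopsis and Section 3.2.1 state that "the combination is anticipated to be well-tolerated in a relapsed or refractory CLL population where cytopenias are common".
- **Data.** The Section 2 schedule has hematology at screening, on Lead-in Day 1, on Days 1, 8, 15 and 22 of Cycles 1 and 2, and at later cycle visits.

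**The concern.** Section 6.1 opens by defining an adverse event whether or not it is thought related to the product. The disease exclusion brings attribution back, and does so at the recording step. A low neutrophil or platelet count in a treated CLL patient has two candidate causes, marrow disease and drug. If the investigator chooses disease and does not find the count worse than expected, no adverse event exists. The per-drug causality assessment in Section 10.4 cannot recover an event that was never recorded.

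No threshold is given for what is expected in a patient who is already cytopenic. Appendix 5 adds that cytopenias cannot define progression during therapy. An on-treatment cytopenia attributed to CLL can therefore count neither as progression nor as toxicity.

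Toxicity of the combination is a secondary objective. The Synopsis and Section 3.2.1 describe both drugs as not myelosuppressive, while the protocol quotes grade 3-4 neutropenia for each. Readers will look to this trial for whether the combination adds to those rates. As planned, the answer would pass through the judgment of investigators who know the treatment, with no concurrent control.

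**Working it through.** **1. The plan's own figures.** No figure is stated for toxicity. The only design calculation is the efficacy rule in Section 10.3.2 (19 or more responses of 31; 0.470 against 0.670). Exact binomial tails give error rates of 0.0786 and 0.1915, matching the stated 0.079 and 0.192. Nothing in this point changes them.

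**2. One count followed through the rules.** Section 5.2 excludes platelets of 30 x 10⁹/L or below, so a patient may enter just above 30. Section 5.5.4 sets grade 4 thrombocytopenia at below 25,000/uL, holds both drugs, and names no cause. Suppose platelets fall from just above 30 to just below 25.
- The inclusion list in Section 6.1 makes this an adverse event if it is felt clinically significant.
- The exclusion list is itself written for clinically significant findings, so significance does not settle the matter. If the count is linked to CLL and not judged more severe than expected, it is not an adverse event.

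The same count can thus interrupt treatment and be either recorded or not, depending on judgment.

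**3. Illustrative size.** Inputs: grade 3-4 neutropenia 6-14% for ofatumumab (Section 3.1), 13% for GSK2110183 at 125 mg (Section 5.1.2), and 31 patients (Section 10.1). Two assumptions are not in the documents: the two risks act independently, and a fraction s of affected patients has no such event recorded.

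True rate = 1 - (1 - 0.13)(1 - p), where p is the ofatumumab rate:
- p = 0.06: 1 - 0.87 x 0.94 = 18.2%, or 5.6 of 31
- p = 0.14: 1 - 0.87 x 0.86 = 25.2%, or 7.8 of 31

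Reported rate = true rate x (1 - s):

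| s | Reported rate | Patients of 31 |
|---|---|---|
| 0 | 18.2-25.2% | 5.6-7.8 |
| 25% | 13.7-18.9% | 4.2-5.9 |
| 50% | 9.1-12.6% | 2.8-3.9 |
| 75% | 4.6-6.3% | 1.4-2.0 |

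At s = 50% the reported rate is no higher than the 13% for GSK2110183 alone. It is not below both single agents throughout: the 9.1% arises when ofatumumab is 6%, and 9.1% exceeds 6%.

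**4. Precision.** Exact 95% intervals are 11.9-44.6% for 8 of 31 and 3.6-29.8% for 4 of 31. They overlap widely, so the adverse-event table alone would not reveal that half the events were missing.

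**The case against.** The strongest case against is that the text already limits the exclusion. Findings more severe than expected remain adverse events, and hematology that worsens from baseline is named in the inclusion list. Section 6.1 also lists exacerbation of a pre-existing condition and exempts only fluctuations that do not worsen. Section 6.2 gives blood dyscrasias as an example of a medically important event. Since entry requires platelets above 30, any grade 4 thrombocytopenia is a worsening from the entry level, and one that stops both drugs is hard to dismiss. This stands in part. It rules out the reading that every laboratory abnormality linked to CLL is removed, and the most severe events are the least likely to be lost. It does not remove the dependence on judgment, because each safeguard is itself an investigator's decision without a stated threshold.

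A reader might also infer that the trial cannot show whether the combination is myelosuppressive. The documents do not support that. Blood counts with a pre-treatment baseline are collected whatever the attribution, and grade-triggered dose holds leave a record. What is missing is a planned analysis of those counts.

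A reader might further infer that counting from the lead-in hides myelosuppression. It does not. Section 10.2 states who is evaluable and from when; events can be separated by date, and counts are scheduled on Lead-in Day 1 and Cycle 1 Day 1. Keeping all treated patients from first dose is a legitimate choice. Closing a combination window at the start of Maintenance could file delayed ofatumumab effects under single-agent GSK2110183; the schedule's own hepatitis B monitoring runs to one year after the last ofatumumab dose. The single-arm design, not the lead-in, limits attribution to the combination.

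**Conclusion.** The point holds as an analysis gap. Because the endpoint rests on adverse events, Sections 6.1 and 6.3.1 allow disease-attributed cytopenias to go unrecorded, and Sections 10.3 and 10.4 plan nothing based on the counts, the reported hematologic toxicity may be too low.

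The size cannot be read from the documents, because they give no value for the unrecorded fraction. The 18-25% true rate and the 14-19%, 9-13% and 5-6% reported rates are illustrations that rest on independence and on assumed fractions of 25%, 50% and 75%. The documents also do not say how the single-agent rates were ascertained, so comparison with them is loose. No sample size, error rate or efficacy conclusion is affected. The gap can be closed without changing conduct, so the change should be made.

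**What to change.** Add to Section 10.4:

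- Neutrophil, platelet and hemoglobin toxicity is also derived from all blood counts, scheduled and unscheduled, regardless of attribution and of whether an adverse event was recorded.
- It is presented as worst post-baseline CTCAE 4.03 grade and as a shift table from the Lead-in Day 1 grade to the worst grade. The shift table is needed because a worst grade alone would count cytopenia present at entry as toxicity.
- The safety population remains all treated patients, from the first dose of GSK2110183.
- Optionally, a descriptive display by lead-in, Treatment Phase and Maintenance accompanies the overall table and does not replace it.

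The adverse-event definitions and the clinical management rules can stay as they are. The cost is a paragraph of text and a few tables from data already collected. The reported cytopenia rate may look less favourable. The tables will show how often counts fell and by how much; without a control group they will not establish the cause.
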